Probabilities $P(\%RSV - \%Placebo > \delta)$ are calculated according to each possible distribution of up to 6 observed events between the 2 groups, as shown in the table below.

Probabilities P (%RSV - %Placebo > δ) according to the distribution of observed events between RSV and Placebo groups

N = Total number of events observed in the 2 arms considered in the analysis (one RSV formulation and Placebo)

P = Bayesian probability calculated in the context of balanced design (20RSV/20PL)

Range = (Pmin - Pmax) where Pmin and Pmax are bayesian probabilities calculated in the context of unbalanced design (22RSV/18PL and 18RSV/22PL respectively)

Given a total number of events observed in blind, these results may help safety signal management by assessing the underlying potential safety issues. For instance, cases may be unblinded once a total of 3 events occur.

16 Signature Page

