4.4.4.3 Duration of the Study

The duration of the study is computed in days as follows: maximum of all participants (date of visit, date of termination form) - minimum for all participants (date of visit 01) +1.

5 Statistical Methods and Determination of Sample Size

The statistical analyses will be performed under the responsibility of the Sponsor's Biostatistics platform using SAS® Version 9.4 software or later.

The results of the statistical analysis will be available in the clinical study report (CSR).

For descriptive purposes, the following statistics will be presented:

Table 5.1: Descriptive statistics produced

Baseline characteristics and follow-up description	Categorical data	Number of participants. Percentage of participants.
	Continuous data	Mean, standard deviation, quartiles, minimum, and maximum.
Clinical safety results	Categorical data	Solicited: Number and percentage (95% CIs) of participants. Unsolicited: Number and percentage (95% CIs) of participants, and number of events.
Immunogenicity / Shedding results	Categorical data (cutoff)	Number and percentage (95% CIs) of participants.
	Continuous data (titer / data)	Log10: Mean and standard deviation. Anti-Log10 (work on Log10 distribution, and anti-Log10 applied): Geometric mean, 95% CI of the geometric mean, quartiles, minimum, and maximum. Graphical representation by Reverse Cumulative Distribution Curve (RCDC) for immunogenicity.
Infectivity results	Categorical data	Number and percentage (95% CIs) of participants.
Efficacy results	Categorical data	Number and percentage (95% CIs) of participants, number of events, Vaccine Efficacy (VE) and 95% CI.

The statistical methodology will be based on the use of two-sided 95% confidence intervals (CI).

The Confidence Interval (CI) for the single proportion will be calculated using the exact binomial method (Clopper-Pearson method, quoted by Newcombe (1), i.e., using the inverse of the beta integral with SAS®).

For immunogenicity results, assuming that Log10 transformation of the titers/titers ratio follows a normal distribution, at first, the mean and the 95% CI will be calculated on Log10 (titers/titers ratio) using the usual calculation for normal distribution (using Student's t distribution with n-1 degree of freedom), then antilog transformations will be applied to the results of calculations, in order to provide geometric mean titers (GMTs) and geometric mean titers ratios (GMTRs) and their 95% CI.

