5.1.1.2 Statistical Methods

The data for any participant infected by laboratory confirmed wt RSV will be excluded from immunogenicity and viral shedding analyses from the date of wt RSV infection.

A short complementary analysis will be done without the exclusion of data to compare results.

Safety

Solicited adverse reactions (ARs), unsolicited AEs (including SAEs), MAAEs and AESIs will be summarized as described in Table 5.1. The main parameters will be described with 95% CI. At least the following parameters will be presented by vaccine group after each and any vaccination, in all participants regardless of baseline serostatus:

- Unsolicited systemic AEs occurring within 30 minutes of administration (immediate unsolicited AEs)

- Solicited administration site reactions and solicited systemic reactions within 28 days after each and any administration according to presence, time period, time of onset, intensity, number of days of presence, action taken, and whether the reaction led to early termination from the study. When more than 1 intensity level is reported within a time period, the highest intensity will be used.
- Unsolicited AEs occurring within 28 days after each and any administration by system organ class (SOC) and preferred term (PT), relationship, intensity, time of onset, duration and whether the AE led to early termination from the study.
- All SAEs that occur throughout the study by SOC and PT, seriousness criteria, time of onset, outcome, relationship, and whether the SAE led to early termination throughout the study
- All MAAEs and AESIs reported within 28 days after each and any vaccination by SOC and PT and relationship

Bayesian approach

A Bayesian approach based on Posterior Distribution may be applied to assess the difference between each RSV formulation and placebo group on the following safety endpoints (and/or other endpoint of interest):

- Any Grade ≥ 3 LRI
- Grade 3 fever

The probability that the difference of percentages of events between one RSV formulation and Placebo is greater than a pre-specified margin (δ) can be calculated based on posterior distribution, using non-informative prior Beta (1,1) (3) and observed binomial data:

Proba (%RSV - %Placebo > δ)

With:

- %RSV = (number of events / number of participants) in RSV group
- %Placebo = (number of events / number of participants) in Placebo group

If this probability is high (e.g., $\geq 80\%$) then it may be recommended to drop the formulation.

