To assess the Bayesian probability that the percentage of events in RSV group is greater than a predefined value (δ) in comparison to Placebo, the posterior distribution of the difference (RSV - Placebo) would be computed using:

- a non-informative prior distribution: incidence of events in each group (p_i) follows uniform distribution (0,1)
- the likelihood of the observed data: Binomial distribution (n_i, p_i), n_i = number of assessed participants in each group, p_i = incidence of the events in each group
- The posterior distribution is the density distribution of the parameter P_i combining 1) the prior distribution and 2) the observed data.

- Posterior distribution: Beta (x_i+1, n_i-x_i+1), where x_i = number of events in each group and n_i = number of assessed participants in each group
- From the density distribution of P_{RSV} and $P_{Placebo}$, determine the density of the groups difference: simulate 1 000 000 pairs of observations and determine the proportion of difference ($P_{RSV} - P_{Placebo}$) $> \delta$.

Immunogenicity

The point estimates and their 95% CI of the following parameters will be presented for RSV A neutralizing antibody titers by D56 for Cohorts 1, 2, 3 and 4, and by D84 for Cohorts 2 and 4, for each vaccine group in RSV-naive participants:

- GMT
- GMTR based on the baseline neutralizing Ab titer
- Seroresponse rates defined as percentage of participants with a ≥ 4 -fold rise in RSV A serum neutralizing antibody titers based on the baseline value.
- Reverse cumulative distribution curves (RCDCs) will be presented
- Pairwise comparisons between vaccine groups may be conducted as exploratory analyses to compare seroresponse rates or GMTs for descriptive purpose.

The 95% CIs of the difference of proportions between 2 groups would be computed using the Wilson Score method without continuity correction. CIs of ratio of GMTs between 2 groups will be computed from the difference in means of log10 transformed titers between 2 groups with normal approximation.

Seroresponse using various thresholds regarding fold-rise or post-vaccination titer value may also be presented, as applicable. 4-fold rise seroresponse rate may be also presented by country/racial origin.

A Bayesian approach may be also applied to assess the seroresponse rate of RSV formulation by calculating the Bayesian probability that the percentage of participants with a ≥ 4 -fold rise in RSV A serum neutralizing antibody titers is greater than a predefined value.

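### The optional Bayesian safety calculation puts a count of events into a binomial model over participants; the numerator should be children with at least one qualifying event

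*SAP*

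**What the plan says.** SAP 5.1.1.2, under the Bayesian approach, defines the two percentages as "RSV = (number of events / number of participants) in RSV group" and "Placebo = (number of events / number of participants) in Placebo group". The posterior in each group is Beta(x_i+1, n_i−x_i+1), "where x_i = number of events in each group and n_i = number of assessed participants in each group". The likelihood is Binomial(n_i, p_i), with "n_i = number of assessed participants in each group, p_i = incidence of the events in each group". The calculation is described as "using non-informative prior Beta (1,1) (3) and observed binomial data".

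The method may be applied. If the probability that the difference exceeds a margin is high, with 80% given as an example, dropping the formulation may be recommended. The SAP fixes no margin. The worked example in Protocol Section 15 uses 5% and 20 participants per group, with 22/18 and 18/22 as unbalanced variants. It adds: "For instance, cases may be unblinded once a total of 3 events occur".

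Elsewhere the SAP keeps the two counts apart. Table 5.1 lists, for safety, "Unsolicited: Number and percentage (95% CIs) of participants, and number of events". The Bayesian seroresponse option in 5.1.1.2 is worded as a percentage of participants. SAP 4.4.1.2.6 lists stridor, rales, tachypnea, acute wheeze, pneumonia and laryngotracheobronchitis individually under lower respiratory illness.

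**The concern.** A binomial count with n_i participants assumes one yes/no outcome per child. The stated x_i does not guarantee that. Lower respiratory signs overlap by definition: Protocol 9.1.1.3.5 describes pneumonia through rales, usually with tachypnea, and croup through inspiratory stridor. One illness could therefore give several qualifying records. Children in Cohorts 2 and 4 are also observed after two administrations. The Bayesian text contains no rule that collapses these records to one per child.

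Correlated records from one child would then carry the weight of independent children. If the extra records are in the vaccine group, the probability of harm is overstated. If they are in the placebo group, a real excess is hidden. Taken literally, x_i could even exceed n_i, and the posterior is then undefined because n_i−x_i+1 is zero or negative. Two programmers, one following the definition of x_i and one following the likelihood, could land on opposite sides of 80% with the same data.

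**Working it through.** **Inputs.** Prior Beta(1,1), posterior form and 80% level: SAP 5.1.1.2. Margin δ = 5%, groups 20/20, 22/18 and 18/22 (RSV/placebo): Protocol Section 15. Cohort 4 at 60 per group and pooled groups of 100 low-dose, 80 high-dose and 120 placebo: SAP 5.5. The 40/40 case pools Cohorts 1 and 2 (20+20 low-dose, 20+20 placebo).

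**Formula.** With x₁ of n₁ in the RSV group and x₀ of n₀ in placebo,

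P = ∫₀^(1−δ) f(q; x₀+1, n₀−x₀+1) · S(q+δ; x₁+1, n₁−x₁+1) dq,

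where f is the Beta density and S the upper-tail probability of the Beta distribution.

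**Reproducing the protocol's figure.** At 20/20 with δ = 5%, the largest probability for a given total arises when all events are in the RSV group:

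| Total events | RSV posterior | Placebo posterior | P |
|---|---|---|---|
| 1 | Beta(2,20) | Beta(1,21) | 0.441 |
| 2 | Beta(3,19) | Beta(1,21) | 0.683 |
| 3 | Beta(4,18) | Beta(1,21) | 0.840 |

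The SAP's own method, one million simulated pairs, gave 0.441, 0.683 and 0.840. Three is the smallest total at which any split reaches 80%. This agrees with the total of three in the appendix example. The appendix's probability table is not in the text available here, so its cells could not be compared.

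**Effect of the counting unit at 20/20, δ = 5%, no placebo events.**
- One child, counted once: 0.441. The same child entered as three events: 0.840.
- Two children, each counted once: 0.683. The same two entered as three events: 0.840.

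**Three RSV events under other conditions** (δ = 5% and no placebo events unless stated):

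| Setting | P |
|---|---|
| 18/22 | 0.885 |
| 22/18 | 0.787 |
| 20/20, one placebo event | 0.659 |
| 20/20, δ = 2% | 0.915 |
| 20/20, δ = 7.5% | 0.749 |
| 20/20, δ = 10% | 0.641 |
| 40/40 | 0.649 |
| 60/60 (Cohort 4) | 0.444 |
| 80/120 (high-dose pooled) | 0.312 |
| 100/120 (low-dose pooled) | 0.168 |

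At 40/40, two children with two signs each (four events) move from 0.441 to 0.802.

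**Opposite direction.** At 20/20, three affected RSV children against one affected placebo child give 0.659. If that placebo child is entered as three events, the result falls to 0.325.

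**After counting each child once.** With no placebo cases and δ = 5%, reaching 80% takes 3 different children at 20/20 (0.840), 4 at 40/40 (0.802), 6 at 60/60 (0.874), 6 at 80/120 (0.802) and 8 at 100/120 (0.856).

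**The case against.** The best reply is that a per-child count was intended. The data are called binomial, p_i is an incidence, and the endpoint is any lower respiratory illness of the stated grade, which reads as yes/no. SAP 5.5 also uses the word event per participant when it gives the chance of observing an event of 3% incidence. In Protocol 5.1.6, the review criteria for Grade 3 fever and lower respiratory illness count participants. All of this is plausible, and it supports the correction: the written definition should match the model. It does not remove the conflict, because x_i is defined twice as events and Table 5.1 treats events and participants as different statistics.

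Recurrent fever is largely dealt with. SAP 4.4.1.1.2 and 4.4.1.1.3 reduce daily records to one maximum intensity per period, and 4.4.1.3 takes the maximum across vaccinations for the after-any-vaccination tables. That leaves mainly different lower respiratory terms in one child. SAP 4.4.1.2.2 takes the highest intensity for a unique term, which does not merge different terms. The Bayesian paragraph cites none of these derivations. It is also fair that no section requires one illness to be entered as several Grade 3 records. The multiple count is possible under the text, not certain.

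A reader might infer that a single child could force a dose to be dropped or the blind to be broken. The documents do not support that. The method is optional, 80% is an example, the three-event total is an illustration, and Protocol 5.1.6 presents the probability as help for a decision that still passes through safety-team review. Under the same section, one participant with a Grade 3 or higher event of special interest, including lower respiratory illness, already meets a review criterion. That child's case would be examined however the Bayesian count is made.

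**Conclusion.** The definition is wrong as written, and its importance is minor. The numerator counts events while the likelihood counts participants, and no stated rule reconciles them. In the protocol's own example the choice of unit moves the probability from 0.44 to 0.84 for one child, or from 0.68 to 0.84 for two, across the illustrative 80% level.

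That crossing rests on three assumptions: separate Grade 3 or higher records for concurrent signs, no placebo events, and groups of about 20 with a margin near 5%. Three events fall short at 22/18, with one placebo event, at a 7.5% margin and in the 40/40, 60/60 and fully pooled groups. Larger multiple counts can still matter there, as the four-event case at 40/40 shows. It would go too far to call this a faulty stopping rule or a faulty unblinding trigger, because the plan contains neither in binding form.

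**What to change.** In SAP 5.1.1.2, define x_i as the number of participants with at least one qualifying event (for the endpoint as the SAP words it) in the evaluation period. Define both percentages as those participants divided by participants assessed, so that numerator, denominator and likelihood share one unit. State the evaluation period, so that a child with events after both vaccinations counts once within it. In Protocol Section 15, change the event totals in the table legend and in the unblinding illustration to numbers of participants with an event.

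The cost is a few words in each document and a one-record-per-child step in the safety programming. No new data, sample size or clinical criterion is involved. The probabilities for given counts do not change, only what is counted.

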	
• The final unblinded analysis will address the objectives on all participants (Cohorts 1, 2, 3 and 4) including the post season follow up. 
All analyses will be descriptive; no hypotheses will be tested.
 
During a cohort's safety review and/or at the end of the study, a Bayesian approach based on posterior distribution of the difference in incidence between groups may be applied.
 
The Safety Analysis Set will be used for safety analyses. Immunogenicity analyses will be performed on the Full Analysis Set and, on the Per-Protocol Analysis Set for main immunogenicity parameters.
 
All endpoints will be summarized by vaccine group. For the main parameters, 95% confidence intervals (CIs) of point estimates will be calculated using the normal approximation for quantitative data, and the exact binomial distribution (Clopper-Pearson method) for proportions.
 
Calculation of Sample Size:
 
No sample size calculation was done as there are no statistical hypotheses in this study.
 
A total of 300 participants are planned to be enrolled into 1 of the 4 cohorts sequentially:
 
• Cohort 1 (1 administration): 40 participants, i.e., 20 per vaccine group (RSV low-dose or placebo)• Cohort 2 (2 administrations): 40 participants, i.e., 20 per vaccine group (RSV low-dose or placebo)• Cohort 3 (1 administration): 40 participants, i.e., 20 per vaccine group (RSV high-dose or placebo)• Cohort 4 (2 administrations): 180 participants, i.e., 60 per vaccine group (RSV high-dose or RSV low-dose or placebo).
--	--

Table of Study Procedures for Cohorts 1 and 3

Phase I/II Study, 4 Planned Visits, 30 (32) non-visit telephone contacts, 1 Vaccination, 3 Planned Blood Samples, 1 Planned Nasal Swab, up to a Maximum of 12 Months of Participation per Participant

Visit (V) / Contact	Visit 01	Phone contacts 1 - 6	Visit 02	Phone contacts 7 - 16	Phone Contact 17	Phone contact 18	Visit 03	Phone contacts 19 -30 (32) ‡‡	Visit 04 §§	Illness Visit(s) Visit 99***
Study timelines - Days(D)	D0	Daily (x6)	D7	Three times weekly (x10)	D29 (+1)	D42 (+1)	D56 (+7)	Every 2 weeks	1 – 30 Apr (NH)	
In-person visit	X		X				X		X	X
Non-visit contact*		X		X	X	X		X		
Informed consent	X									
Demography data	X									
Inclusion / Exclusion criteria	X									
Medical history and physical examination	X									
Vital signs [†]	X		X				X			X
COVID-19 test	X									X
Interim history			X				X			X

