5.1 Statistical Methods

Statistical analyses will be conducted by cohort and cohorts pooled, as applicable on specific periods of time (e.g., D0-D56 after vaccination 1 for Cohorts 1, 2, 3 and 4; D56-D84 after vaccination 2 for Cohorts 2 and 4).

When applicable, analyses will be presented by baseline serostatus and overall.

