5.1.2.2 Statistical Methods

Safety

The point estimates and their 95% CI of the following parameter will be presented 7 days after each vaccination (D7 for Cohorts 1, 2, 3 and 4, and D63 for Cohorts 2 and 4) for each vaccine group by baseline serostatus:

- Proportion of participants with detectable/quantified virus shedding
- Arithmetic mean of vaccine virus shedding measured by [REDACTED]

Infectivity

The point estimate and its 95% CI of the following parameters will be presented after vaccination 1 (D56) for Cohorts 1, 2, 3 and 4, and after vaccination 2 (D84) for Cohorts 2 and 4 for each vaccine group by baseline serostatus:

- Proportion of vaccinees infected with the vaccine virus. Infection defined as detection of vaccine virus strain in nasal swab by [REDACTED] and / or a \geq 4-fold rise in RSV A serum neutralizing antibody titers or RSV serum anti-F IgG antibody titers.

Immunogenicity

The point estimates of GMT and GMTR and their 95% CI will be presented by vaccine group for the following endpoints:

- RSV A serum neutralizing antibody titers by D56 for Cohorts 1, 2, 3 and 4, and by D84 for Cohorts 2 and 4, in RSV-experienced participants
- RSV serum anti-F IgG antibody titers by D56 for Cohorts 1, 2, 3 and 4, and by D84 for Cohorts 2 and 4 by baseline serostatus.
- RSV A serum neutralizing and anti-RSV F IgG antibody titers after RSV season or at least 5 months after last vaccine administration by baseline serostatus.

Seroresponse using various thresholds regarding fold-rise or post-vaccination titer value may also be presented, as applicable.

Main immunogenicity analyses will be presented by baseline serostatus and age group (< 12 months *versus* \geq 12 months).

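### The interval for a ratio of two GMTs is specified by a normal approximation, although one-group GMTs use Student's t; read literally, it is slightly too narrow in the RSV-naive comparisons within Cohorts 1 to 3

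*SAP*

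**What the plan says.** The opening text of SAP section 5 sets the general rule: "The statistical methodology will be based on the use of two-sided 95% confidence intervals (CI"). For one-group GMTs and GMTRs it works on the log10 scale "using Student's t distribution with n-1 degree of freedom" and back-transforms.

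For the ratio of two GMTs, SAP 5.1.1.2 (Immunogenicity) says the interval is "computed from the difference in means of log10 transformed titers between 2 groups with normal approximation". Protocol 12.1.1.2 has the same wording. Neither gives a quantile, degrees of freedom, or a choice between pooled and separate variances.

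The ratios are optional: "Pairwise comparisons between vaccine groups may be conducted as exploratory analyses to compare seroresponse rates or GMTs for descriptive purpose". This line stands in the list for RSV-naive participants.

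On group size, SAP 5.1 states: "Statistical analyses will be conducted by cohort and cohorts pooled". SAP 5.1.2.2 adds: "Main immunogenicity analyses will be presented by baseline serostatus and age group". SAP 5.5 gives 20 per vaccine group in each of Cohorts 1, 2 and 3, and 60 per vaccine group in Cohort 4.

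The protocol synopsis uses the same phrase more loosely: "95% confidence intervals (CIs) of point estimates will be calculated using the normal approximation for quantitative data". Those include the one-group intervals that the SAP computes with t.

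**The concern.** Two intervals built from the same log10 titers are described in different ways. The one-group interval allows for the SD being estimated. The two-group interval, read literally, does not. A 1.96 multiplier with an estimated SD always errs in the same direction: the interval is too short. The error grows as the groups shrink, and the plan does call for analyses by cohort, with 20 per arm.

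The trial tests no hypotheses, and Protocol 5.1.2 bases dose selection on a descriptive comparison. A GMT ratio with its interval, if produced, would be read directly as evidence for or against a difference between groups. Its 95% label should therefore be right.

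**Working it through.** **The plan's own figures.** The plan gives no number for the ratio interval beyond the nominal 95%. The counts in SAP Table 5.2 reproduce exactly as group size times rate; for example, at 5% experienced, 100 × 0.05 = 5 low-dose and 80 × 0.05 = 4 high-dose participants.

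**Group sizes.** The 5% to 35% RSV-experienced range is from SAP 5.5.
- Cohorts 1 to 3, naive per arm: 20 × 0.65 = 13 to 20 × 0.95 = 19.
- Cohort 4, naive per arm: 60 × 0.65 = 39 to 60 × 0.95 = 57.
- Pooled naive after vaccination 1, at 35% experienced: 65 low-dose, 52 high-dose, 78 placebo.
- Cohort 1 to 3 arm, naive and split by age: 13/2, about 7, assuming half in each age stratum. The documents give no age split. Seven is also the RSV-experienced count per arm at 35% (20 × 0.35).
- Pooled RSV-experienced at 5%: 5 low-dose against 4 high-dose.

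**Formulae.** Assume normal log10 titers and equal SDs. With a pooled variance and df = n1 + n2 − 2:
- true coverage of the z interval = 2·F(1.960; df) − 1, where F is the t distribution function;
- shortfall in width = 1 − 1.960 / t(0.975; df).

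The SD cancels, so neither result depends on it.

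| Comparison | n per group | df | t(0.975) | z coverage | z interval too short by |
|---|---|---|---|---|---|
| Cohorts 1–3, naive, 5% experienced | 19 v 19 | 36 | 2.028 | 94.2% | 3.4% |
| Cohorts 1–3, naive, 35% experienced | 13 v 13 | 24 | 2.064 | 93.8% | 5.0% |
| Cohort 4, naive, 35% experienced | 39 v 39 | 76 | 1.992 | 94.6% | 1.6% |
| Pooled naive, high dose v placebo, 35% | 52 v 78 | 128 | 1.979 | 94.8% | 0.9% |
| Only if extended: naive by age, or experienced at 35%, in Cohorts 1–3 | 7 v 7 | 12 | 2.179 | 92.6% | 10% |
| Only if extended: pooled experienced, low v high dose, 5% | 5 v 4 | 7 | 2.365 | 90.9% | 17% |

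**Check with separate variances.** Simulation with an unpooled standard error (200,000 to 400,000 replicates) gave 94.2% at 19 v 19, 93.8% at 13 v 13, 94.7% at 39 v 39, 92.7% at 7 v 7 and 90.8% at 5 v 4. This agrees with the table.

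**On the titer scale.** At 13 v 13 with an assumed log10 SD of 0.5, the ratio is multiplied and divided by 10^(1.960 × 0.5 × √(2/13)) = 2.42 under z, and by 2.54 under t. Over an assumed SD range of 0.3 to 0.7, the pairs run from 1.70 and 1.75 to 3.45 and 3.69.

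**Unequal SDs.** If one SD is twice the other (an assumption), z coverage falls to 93.5% at 13 v 13, 92.0% at 7 v 7 and 88.8% at 5 v 4. The Welch t interval stays at 94.8% to 95.0%.

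**The case against.** The strongest reply is that no 1.96 appears in the documents. The synopsis applies the same phrase to intervals that the SAP computes with Student's t, so the sponsor may well intend t here too. That stands. A reader might infer that the SAP prescribes a z interval, but this is the literal reading and not a certainty. The sentence is still incomplete on either reading: section 5 of the SAP spells out t for one group, while the two-group sentence leaves the quantile and the variance rule open.

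A reader might also infer that the evidence for a difference between doses is overstated in the small cohorts. The design does not support that. Cohorts 1, 2 and 3 each hold one dose and placebo. A within-cohort dose comparison exists only in Cohort 4, where naive groups of 39 to 57 lose under half a point of coverage. Even at the interim minimum of 90 Cohort 4 participants, about 30 per arm, a 35% experienced rate leaves about 20 naive per arm, and 20 v 20 gives 94.3%.

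The 90.9% and 92.6% figures are tempting headlines, but the plan does not clearly call for those comparisons. The pairwise line belongs to the RSV-naive list. For RSV-experienced participants, SAP 5.1.2.2 lists GMT and GMTR by vaccine group and no between-group ratio. Presenting main analyses by serostatus and age group is not a commitment to compute optional ratios in every cell.

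Finally, the other intervals in the plan (one-group t, Clopper-Pearson, Wilson, exact vaccine efficacy) are unaffected, and no decision rule uses a GMT-ratio interval. That also stands, and it keeps this a minor point.

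**Conclusion.** The point holds as a small, conditional one. If the normal approximation means a 1.96 multiplier, nominal 95% intervals for RSV-naive vaccine-versus-placebo GMT ratios within Cohorts 1 to 3 cover about one percentage point too little. Comparisons with 39 or more per group are barely affected. Shortfalls of two to four points would need ratios in cells that the plan does not clearly include.

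The figures assume normal log10 titers, equal SDs except where stated, and no dropout or exclusions, which would make the groups smaller. What the documents establish is an underspecified method that is inconsistent with the one-group rule. They do not establish that reported intervals will be materially wrong.

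**What to change.** In SAP 5.1.1.2 and Protocol 12.1.1.2, replace the reference to a normal approximation with a two-sample t interval for the difference in mean log10 titers, back-transformed to a ratio, and name the variance rule and degrees of freedom. Separate variances with Welch-Satterthwaite degrees of freedom is the safer choice, because it also holds when SDs differ. A pooled t with n1 + n2 − 2 degrees of freedom is acceptable if equal variances are assumed. If the protocol is not to be amended, the SAP can carry the change and record it in section 5.7. It would also help to say in which subgroups these ratios will be produced.

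The cost is a sentence and a standard procedure option. With the pooled t, intervals widen by about 5% at 13 v 13 and under 2% at 39 v 39. No new data are needed.
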